9.9 Safety assessment

For longitudinal safety variables (laboratory analysis data) mean, standard deviation, median, minimum and maximum should be provided. For nominal variable group frequencies and percent of patient for each demographic category should be provided.

All AE should be presented as a list and coded in accordance to the MedDRA terminology of lower grade (version on data lock point). AE started before administration of the study product

should not be included into analysis.

Frequency of all AE should be summarized (number and percent of patients in which AE were reported at least once during the study) concerning interaction with the study product, assessed by investigator, and by severity grade.

For comparison of AE appearance in the study groups χ^2 test of exact Fisher test is planned to be applied, for comparison of manifestation rate Mann-Whitney U test will be applied.

Laboratory parameters (total blood count and blood biochemistry, urinalysis), vital parameters will be assessed separately to each group with the following comparison using paired Student t-test for connected samples (for parameters with normal distribution) or using non-parametric Wilcoxon signed rank test for connected samples (for parameters with ordinary scale type or in case of significant distribution deviations from normal).

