Unfortunately despite widespread distribution of the disease no optimum approaches to OAB treatment are available nowadays. This is connected, from one side, with wide spectrum of clinical manifestations of the disease, and, from other side – with insufficient efficiency of medicinal products and huge amount of side effect, caused by them. There are three main directions in OAB treatment nowadays [3]: 1) pharmacotherapy; 2) drug-free treatment; 3) surgical treatment. According to ICS recommendations, pharmacological therapy is prioritized in OAB treatment. Medical treatment of OAB patients is principally directed onto regain of control over accumulative capacity of the urinary bladder. Anticholinergic drugs (M-cholinergic antagonists) are the standard medicines for these indications because it is documented that acetylcholine-driven stimulation of postganglionic muscarinic receptors of detrusor is the main reason for both normal and involuntary constrictions of urinary bladder. [4]

Action mechanism of anticholinergic drugs consists of blocking of post-synaptic M₂, M₃ muscarinic cholinoreceptors of urinary bladder detrusor. [5]

Clinical trials indicated that anticholinergic agents bring to decreases frequency of OAB symptoms within 1-2 weeks of treatment, and maximum effect is acquired by 5-8 weeks of treatment. In the same time treatment assumes prolonged courses. Despite this in many cases of monotherapy with anticholinergic agents after their withdrawal OAB symptoms relapse is observed, that makes essential their constant intake with the object of adequate therapeutic effect maintenance. [6]

Medicinal product under brand name Uritos[®] (Imidafenacin) manufactured by Internal document of Kyorin Pharmaceutical Co., Ltd., was approved in Japanese pharmaceutical market in 2007 for treatment of overactive bladder in the form of film-coated tablets 0.1 mg. After the year the product was approved in South Korea. At the present time post-marketing examinations have been finished, confirming efficient application of the product for the indication of OAB and good safety profile.

Objective of this study is confirmation on non-inferiority and validation of similar safety profile of new anti-muscarinic medicinal product Uritos[®] (Imidafenacin) manufactured by Kyorin

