2.3.1 Expected side effect of the study product [13]

Adverse reactions towards imidafenacin, including deviations of laboratory parameters, were reported in 533 (45.5%) of 1172 studied cases. Primary adverse reactions included: thirst/dry mouth in 368 cases (31.4%), constipation in 98 cases (8.4%), photophobia in 18 cases (1.5%), blurred vision in 16 cases (1.4%), drowsiness in 16 cases (1.4%), gastric discomfort in 13 cases (1.1%), increased triglycerides level in 13 cases (1.1%) and increased activity of gamma-glutamyl transferase (GGT) in 12 cases (1.0%).

In additional clinical trials of dosage and application adverse reactions were reported, including deviations of laboratory parameters, in 215 (49.4%) of 435 studied cases. Primary adverse reactions included: thirst/dry mouth in 164 cases (37.7%), constipation in 59 cases (13.6%), residual urine volume in eight cases (1.8%), leukocyturia in seven cases (1.6%), gastric discomfort in six cases (1.4%), headache in five cases (1.1%) and dysuria in five cases (1.1%).

Clinically significant adverse reactions:

- Acute glaucoma (occurrence rate 0.06%). Because acute glaucoma morbidity rate due to increased intraocular pressure was reported, patients require close monitoring. In case of this event appearance product intake should be stopped and correspondent measures should be undertaken.
- Retention of urine (frequency is not known: based on spontaneous reports). Patients should be under close monitoring due to the risk of urine retention. In case of this event appearance product intake should be stopped and correspondent measures should be undertaken.
- Liver abnormality: increased level of liver enzymes (frequency is not known: based on spontaneous reports). Liver function impairment may present with increased alanine aminotransferase (ALT), aspartate aminotransferase (AST) and bilirubin values. Patients should be closely monitored and in case of any abnormalities appearance product intake should be

stopped and correspondent measures should be undertaken.

Clinically significant adverse reactions (similar products):

- Paralytic intussusceptions: cases of paralytic ileus were reported after administration of similar products (other medicines for OAB treatment), so patients require close monitoring. In case of correspondent symptoms appearance, including constipation and abdominal distension, product intake should be stopped and correspondent measures should be undertaken.

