3 OBJECTIVES AND TASKS OF THE STUDY

Study objective:

Assessment of clinical efficiency and safety of the medicinal product Uritos® (Imidafenacin) in comparison to the medicinal product Urotol (tolterodine) for the indication of overactive bladder (OAB) treatment.

Study objectives:

- Determination of clinical efficiency of the product Uritos® (Imidafenacin) in comparison with the product Urotol (tolterodine) according to its influence on urination frequency and number of urinary incontinence episodes. Safety assessment of the medicinal product

Uritos® (Imidafenacin) in comparison to the medicinal product Urotol (tolterodine).

- Perform safety assessment of the medicinal product Uritos® (Imidafenacin) in comparison to the medicinal product Urotol (tolterodine).

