9.3 Significance level applied

All analysis types used in the study will be performed at the statistical significance level < 0.05 if otherwise noted.

During assessment of significance of discrepancies in primary endpoint access one-sided 97.5% confidence interval will be applied.

Two-sided 95% confidence intervals will be applied during description and testing of other data.

9.4 Interim analysis and study cessation criteria.

Not applicable

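### Section 2 aims to validate a similar safety profile, but section 9.9 compares adverse events by difference tests with no named effect measure, margin or rule, so a non-significant result could not support that aim.

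*Combined protocol and SAP*

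**What the plan says.** The safety aim appears in two forms. The background narrative in section 2 says: "Objective of this study is confirmation on non-inferiority and validation of similar safety profile of new anti-muscarinic medicinal product". The formal objectives in section 3 are more modest: "Perform safety assessment of the medicinal product Uritos® (Imidafenacin) in comparison to the medicinal product Urotol (tolterodine". The synopsis objectives likewise ask for a comparison and do not use the word similar.

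Section 9.9 sets out the AE analysis:
- On listing and coding: "All AE should be presented as a list and coded in accordance to the MedDRA terminology of lower grade".
- On summaries: "Frequency of all AE should be summarized (number and percent of patients in which AE were reported at least once during the study", broken down by relationship to study product and by severity.
- On comparing arms, immediately after the chi-square symbol: "test of exact Fisher test is planned to be applied, for comparison of manifestation rate Mann-Whitney U test will be applied". The term manifestation rate is not defined; severity is the likely meaning.

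Section 9.3 adds a general rule: "Two-sided 95% confidence intervals will be applied during description and testing of other data". The synopsis has an equivalent line for comparisons other than the primary one, shortly before it repeats the chi-square/Fisher sentence.

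The only margin in the document is the 0.8 episodes per day for urination frequency (section 9.2). There is no safety margin and no rule for concluding similarity.

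**The concern.** A chi-square, Fisher or Mann-Whitney test asks whether the data contradict equality. Failing to contradict it is not evidence of similarity, because a small or imprecise study fails in the same way. The protocol applies the right logic to efficacy, with a margin, a directional hypothesis and a confidence bound. Section 9.8 also carries two-sided intervals into the other efficacy comparisons. Section 9.9 does nothing comparable for AEs. A programmer working from it would produce counts, percentages and p-values. If an interval were added under section 9.3, nothing says whether it would be for a risk difference, a ratio or a single proportion.

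What is at stake is the safety statement in the report of a trial intended for registration. Section 2 asks for a conclusion about similarity, and the named analysis cannot deliver one.

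**Working it through.** **The plan's own sample size.** Section 9.2 sizes the trial on urination frequency: 2 × 2.12² × (0.84 + 1.96)² / 0.8² = 110.1, rounded up to 111 per arm, which is the plan's figure. About 300 are to be randomized, 150 per arm. There is no sample size, power or precision figure for safety to reproduce.

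**Inputs**
- n = 150 per arm. The safety population in section 9.7 is every randomized patient with at least one dose, so this is the planned maximum.
- Rates from section 2.3.1 for imidafenacin: thirst/dry mouth 368/1172 = 31.4%; constipation 98/1172 = 8.4%.
- Assumption: the same rates in both arms, because no tolterodine AE rates are given.
- Assumption: two-sided tests at 5%. Section 9.3 gives the 0.05 level but not the sidedness of the safety tests.

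**Precision of the risk difference**

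Half-width = 1.96 × √(2p(1 − p)/n)
- Thirst/dry mouth: 1.96 × √(2 × 0.314 × 0.686 / 150) = 1.96 × 0.0536 = 0.105, or 10.5 points.
- Constipation: 1.96 × √(2 × 0.084 × 0.916 / 150) = 1.96 × 0.0320 = 0.063, or 6.3 points.

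Two ranges show how far these depend on the inputs:
- With the rates from the additional dosage trials in section 2.3.1 (37.7% and 13.6%), the half-widths are 11.0 and 7.8 points.
- With 111 per arm and the main rates, they are 12.2 and 7.3 points.

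**Power of the named tests**

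The contrast of 31.4% versus 41.4% is an assumption: 10 points, or 10/31.4 = 32% more in relative terms.
- Standard error under equality, at the mean rate 0.364: √(2 × 0.364 × 0.636 / 150) = 0.0556.
- Standard error under the contrast: √((0.314 × 0.686 + 0.414 × 0.586) / 150) = 0.0553.
- Chi-square power = Φ((0.10 − 1.96 × 0.0556) / 0.0553) = Φ(−0.16) = 0.44.
- Exact Fisher power by enumeration: 0.39.
- For a 10-point rise from 37.7%, chi-square power is 0.42. With 111 per arm, from 31.4%, it is 0.34.
- For constipation, an assumed 8.4% versus 13.4% gives 0.28 by chi-square and 0.23 by Fisher.

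**An example of what the p-value conceals**

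Suppose 47/150 versus 62/150 patients report thirst/dry mouth (31.3% versus 41.3%). Chi-square gives p = 0.072 and Fisher p = 0.093, so neither is significant. The risk difference is 10.0 points with a 95% interval from −0.8 to +20.8.

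**Could this size exclude an excess, if a margin were set?**

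With one-sided 0.025, 80% power and equal true rates, n per arm = 2p(1 − p)(1.96 + 0.84)² / margin², computed with unrounded normal quantiles. All margins are assumptions.

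| Event | 5 points | 10 points | 15 points |
|---|---|---|---|
| Thirst/dry mouth, 31.4% | 1353 | 339 | 151 |
| Constipation, 8.4% | 484 | 121 | 54 |

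At about 150 per arm, a 10-point margin for constipation is within reach and a 15-point margin for thirst/dry mouth is borderline. Tighter margins are out of reach.

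**The case against.** The strongest reply is that the plan already promises intervals. Section 9.3 and the synopsis call for two-sided 95% intervals beyond the primary endpoint, and a general rule need not be repeated in every subsection. That stands to this extent: it would be wrong to say the plan as a whole contains only difference tests. It does not close the gap, because no AE quantity is named for an interval to be built around.

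The second reply is that similarity appears only in the background narrative, while the formal objectives ask for a comparison. That is correct, and it means that aligning section 2 with section 3 is an acceptable remedy. As written, the two sections differ.

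Third, modest power for AEs in a trial sized on efficacy is normal and not in itself a planning fault. I agree. The figures above show what a non-significant test would leave open. They are not an argument for more patients.

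A reader might also infer that the tests will be run on lowest-level MedDRA terms, so that thirst and dry mouth are split and tested separately. The text does not support this. Section 9.9 attaches that level to listing and coding and names no level for summaries or tests. Section 8.3.3 treats dry mouth as one named event with its own severity scale. Nothing gives a basis for any particular split.

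**Conclusion.** The concern holds in this form: the section 2 aim of validating a similar safety profile has no matching analysis. Section 9.9 names difference tests for AEs, the general interval provision is not linked to an AE effect measure, and no margin or rule defines similar. At 150 per arm a non-significant result would remain compatible with differences of roughly 10 points in thirst/dry mouth and 6 points in constipation, and power against an assumed 10-point rise in thirst/dry mouth is about 44%. These figures rest on imidafenacin rates in both arms, two-sided tests, simple large-sample intervals and full recruitment into the safety population.

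Two stronger readings go too far. One is that the sponsor will read p > 0.05 as similarity: no section says so, and the risk arises only because no rule is given. The other is that the design cannot show similarity at all: that depends on the margin, and the plan sets none.

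This is a low-cost improvement to the analysis text and does not call the design into question.

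**What to change.** Amend section 9.9 so that the main between-arm AE summary is the risk difference, imidafenacin minus tolterodine, with a two-sided 95% confidence interval, for:
- any AE related to study product;
- thirst/dry mouth combined, as in section 2.3.1, with the contributing coded terms listed in advance;
- constipation;
- AEs leading to withdrawal.

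Keep the chi-square/Fisher and Mann-Whitney tests as descriptive. This also gives the interval provision in section 9.3 a defined use for AEs. The same edit can state the MedDRA level used for AE tables, which is at present left open.

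Then do one of two things: state in section 9.9 that similarity will not be concluded from p > 0.05, and give the expected precision (about ±10.5 points for thirst/dry mouth and ±6.3 for constipation, under the assumptions above); or reword the section 2 sentence to match the comparative objective in section 3.

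The cost is a few lines of analysis text, a few more table columns and a more cautious safety claim. No additional patients, visits or data are needed.

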	
Sample containing 222 patients (111 per study group) is considered to be sufficient for proof of alternative hypothesis (rejection of null-hypothesis) at the significance level 97.5% and study strength 80%. With due consideration of withdrawal during treatment total amount of patients to be randomized is about 300 (150 patients per study group).
 
For treatment efficiency assessment (primary endpoint) one-side 97.5% confidence interval for arithmetic mean values of primary endpoint will be calculated. In other cases of comparison two-sided 95% confidence intervals will be utilized.
 
Changes will be considered as significant at $p < 0.05$.
 
For comparison of AE appearance in the study groups χ^2 test of exact Fisher test is planned to be applied, for comparison of manifestation rate Mann-Whitney U test will be applied.
 
Laboratory parameters (total blood count and blood biochemistry, urinalysis), vital parameters will be assessed separately to each group with the following comparison using paired Student t-test for connected samples (for parameters with normal distribution) or using non-parametric Wilcoxon signed rank test for connected samples (for parameters with ordinary scale type or in case of significant distribution deviations from normal).

--	--

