8 SAFETY ASSESSMENT

8.1 List of safety parameters

- 1) Frequency for development of adverse events (AE) and serious adverse events (SAE).
- 2) Frequency of development of AE and SAE, depending on application of the product.
- 3) Frequency of development of AE and SAE, bringing to treatment cessation/withdrawal from the study.
- 4) Residual urine volume assessment using US-examination of the bladder at the study visits against study start visit.
- 5) Changes of laboratory parameters, ECG parameters and vital parameters assessment.

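### Laboratory and vital-sign changes are tested only within each arm, so mean changes are never formally compared between imidafenacin and tolterodine

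*Combined protocol and SAP*

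**What the plan says.** Section 3 and the synopsis set the objective as the safety of imidafenacin in comparison with tolterodine. Section 2 says the trial seeks "validation of similar safety profile of new anti-muscarinic medicinal product". Section 8.1 lists among the safety criteria "Changes of laboratory parameters, ECG parameters and vital parameters assessment".

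For laboratory and vital-sign parameters, Section 9.9 gives one inferential rule: they "will be assessed separately to each group with the following comparison using paired Student t-test for connected samples", "or using non-parametric Wilcoxon signed rank test for connected samples" for ordinal or clearly non-normal data. The synopsis repeats the rule.

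Between-arm tests are named elsewhere. Section 9.9 gives chi-square or Fisher's exact test "For comparison of AE appearance in the study groups" and Mann-Whitney for their severity or rate. Section 9.8 gives ANCOVA, t-tests or Mann-Whitney for efficacy. Section 9.1.1 tabulates data by treatment group, and Section 9.9 adds summary statistics for laboratory data. Section 9.3 promises two-sided 95% confidence intervals for the remaining data but does not say of what contrast.

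Residual urine volume is a separate criterion in Section 8.1: "Residual urine volume assessment using US-examination of the bladder at the study visits against study start visit". Section 9.9 names no method for it or for ECG parameters.

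**The concern.** A paired t-test or signed rank test asks whether an arm changed from its own baseline. It does not use the randomised comparison, so the answer mixes drug effect with time trend and regression to the mean. Here that mixing is hard to dismiss:

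- There is no placebo arm (Section 2.3.5). The tolterodine arm is the only control for time, and the rule does not use it for these parameters.
- Table 5 shows no laboratory tests at Visit 2, so the screening value is the only pre-treatment one. Section 5.2 applies entry limits to screening ALT, AST, bilirubin and creatinine, which favours regression to the mean in the within-arm change.

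The natural way to read two within-arm results is to set the p-values side by side, and that is not a test of a difference. Equal drugs can look different if one arm crosses 0.05 and the other does not. Unequal drugs can look alike if both cross it. Neither pattern supports or refutes a similar safety profile.

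**Working it through.** **Plan's own figure.** No figure is stated for the safety tests. Arm size comes from the primary-endpoint calculation in Section 9.2: SD 2.12, margin 0.8, z-values 0.84 and 1.96.

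n = 2 × 2.12² × (0.84 + 1.96)² / 0.8² = 2 × 4.4944 × 7.84 / 0.64 = 110.1, rounded up to 111 per arm. This reproduces the plan. (The denominator prints as 0.02, possibly a typing or extraction error; 0.8² = 0.64 is what gives 111.) Randomised size is 150 per arm.

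**What the named tests can do.** Both are one-sample tests on within-patient differences. If the phrase about a subsequent comparison was meant as arm against arm, patients in different arms are not paired and neither test applies. The text needs correcting on either reading.

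**Same true change in both arms.** Let d be the true mean change divided by the SD of change. The paired t-test at two-sided 0.05 has power p from the noncentral t distribution with n-1 degrees of freedom and noncentrality d√n. The arms are independent, so

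P(exactly one arm significant) = 2p(1-p).

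The documents give no SDs or expected changes for these parameters, so d is an assumption and is shown as a range (percentages use unrounded p):

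| d | p, 111/arm | exactly one, 111/arm | p, 150/arm | exactly one, 150/arm |
|---|---|---|---|---|
| 0 | 0.050 | 9.5% | 0.050 | 9.5% |
| 0.1 | 0.181 | 29.7% | 0.229 | 35.4% |
| 0.15 | 0.347 | 45.3% | 0.447 | 49.4% |
| 0.2 | 0.551 | 49.5% | 0.682 | 43.4% |
| 0.3 | 0.880 | 21.2% | 0.955 | 8.7% |
| 0.4 | 0.987 | 2.6% | 0.998 | 0.4% |

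Worked line: d = 0.2, n = 111 gives p = 0.551, and 2 × 0.551 × 0.449 = 0.495.

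**Check by simulation.** In 20,000 trials at d = 0.2 in both arms and 111 per arm, exactly one arm was significant in 49.3%. A two-sample t-test on change rejected in 5.3%.

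**Across parameters.** Section 8.2 gives 10 chemistry analytes, 3 vital signs and at least 4 blood-count values, so at least 17. With no true change in either arm, one post-baseline visit and independence assumed, the expected number of one-arm-only results is 17 × 0.095 = 1.6, and P(at least one) = 1 - 0.905^17 = 82%.

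**The opposite error.** With assumed true changes of 0.7 SD and 0.3 SD at 111 per arm, both arms are significant 88% of the time. Two significant arms look alike, yet they differ by 0.4 SD, which a between-arm test would detect with 85% power.

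**Precision of a between-arm estimate.** Half-width of the 95% CI ≈ 1.96 × √(2/n): 0.26 SD of change at 111 per arm and 0.23 SD at 150. The difference detectable with 80% power is (1.96 + 0.84) × √(2/n): 0.38 SD and 0.32 SD.

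**The case against.** The strongest reply is that comparative safety is already covered in part. Section 8.3.1 counts clinically significant laboratory values, changes from baseline and vital-sign findings as adverse events, and Section 9.9 compares adverse events between arms. Tables by arm let a reader compare means by eye. This stands: a reader might infer that comparative safety goes unanswered for these parameters, and the documents do not support that. What is missing is a formal comparison of mean change. The adverse-event route does not replace it, because it admits only findings judged clinically significant, by investigators who know the treatment (Section 4.3.2).

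Three other strong readings go beyond the documents:

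- That residual urine volume and QTc are also tested only within arms. The paired-test sentence names blood count, biochemistry, urinalysis and vital signs. The criterion in Section 8.1 defines a change from the start visit; it is not an analysis rule. For these measures the gap is that no method is stated.
- That within-arm results will be misread. Nothing in the plan says one-arm significance will be called a drug difference, so the risk is that it can happen.
- That equal drugs will often look different. A figure near 50% needs p near 0.5, hence a modest real change in both arms. With no change it is 9.5%, and at 0.4 SD it is under 3%.

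The wording may be a translation of an intended subsequent comparison of groups. Within-arm testing is the likelier reading, not a certain one, but the named tests fail either way. The general promise of 95% intervals does not help, because no between-arm contrast is named.

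It is also fair that no safety hypothesis, margin or power is set, and that many between-arm intervals bring their own chance findings: with 17 independent parameters at one visit, 1 - 0.95^17 = 58% for at least one interval excluding zero under no difference. That is a reason to label the estimates exploratory, not to keep the within-arm tests.

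**Conclusion.** The point holds for laboratory and vital-sign parameters. The stated inferential method cannot answer the trial's comparative question about mean change in them, and no other section supplies one that does. The primary endpoint and the between-arm comparison of adverse events are unaffected.

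The size depends on an unstated step, reading the two within-arm p-values against each other, and on assumed effect sizes. Read that way, the chance of an apparent difference between equal drugs is 9.5% per parameter with no change and peaks near 50%, against about 5% for a direct between-arm test. For residual urine volume and ECG parameters the finding is narrower: Section 9.9 names no method.

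**What to change.** In Section 9.9 and the synopsis, stop using the within-arm tests as the basis for inference. For each laboratory and vital-sign parameter, report the between-arm difference in change from baseline with a two-sided 95% CI. Use ANCOVA with baseline as covariate and treatment as factor, as Section 9.8 already does for efficacy, or a rank-based method for skewed or ordinal variables. State which post-baseline visits are covered (Visits 5 and 6 for laboratory data), and that the intervals are unadjusted and exploratory. Keep within-arm changes as descriptive tables, without p-values.

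Add a sentence applying the same summary to residual urine volume and ECG parameters.

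The cost is plan wording, with the protocol amendment that Section 9.6 requires for a change of the analysis plan, and one standard table per parameter. All the data are already scheduled for collection, and no extra patients or visits are needed.
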